Alcohol use will be measured with the Alcohol Use Disorders Identification Test (AUDIT-C). This three-item measure queries individuals about the quantity and frequency of use as well as binge drinking episodes and has been extensively validated as a screening tool for identifying use disorders in medical populations.⁶²

Smoking status will be assessed by three standard questions addressing quantity, frequency, and recency of smoking established by the Center for Health Quality, Outcomes, and Economic Research (CHQOER) for the VA administered as part of a large health survey of Veteran health behaviors.

Internal Study Evaluations/Process Measures

Treatment engagement and adherence will be assessed using the Psychosocial Treatment Compliance Scale (PTCS).⁴¹ The PTCS is a 17-item, therapist-rated scale of compliance and perceived treatment engagement with psychosocial interventions. Although initially designed for individuals with serious mental illness, the items have broader applicability to other populations. The scale is comprised of two subscales (participation and attendance). Sample items (paraphrased) include “was able to remember the contents/skills taught in previous sessions”, “was attentive in treatment”. The scale has excellent internal consistency and construct validity.⁴¹

Actual versus planned intervention participation in the VA context will be assessed by the screening log and screening data of all potentially eligible participants. VETPALS facilitators will maintain a weekly log documenting attendance and modality of participation (in-person or telehealth), tardiness or early departures from each session, and completion of homework assignments. These two methods, along with the PTCS, will allow investigators to examine differences in participation by delivery modality, understand retention, and quantify treatment exposure.

Use of supplementary resources will be assessed for both the intervention and control conditions by administering a brief survey coinciding with the end of the intervention sessions. The survey measures the use of supplementary project resources, including the recommended websites and participation in concurrent therapeutic/clinical activities (e.g. therapies, locally available programs such as peer visits, Amputee Support Group, and Amputee Coalition resources). This brief survey also will assess several potential factors in engagement, including perceived credibility of the treatment and perceived self-reported engagement in the treatment.

We will formally assess treatment satisfaction using a pencil and paper satisfaction measure used in the original PALS program. The VETPALS facilitator will not directly administer or collect the satisfaction measure. The Veteran peer amputee or another designee will collect all paper copies and place them in a sealed envelope. The facilitator will deliver these to the PI or Co-PI at the Seattle site either by hand delivery, secure and traceable mail (e.g. UPS), or scanning

PDF copies and uploading to a secure SharePoint. The PI and Co-PI are responsible for reviewing these questionnaires and entering data into the database.

To describe and understand barriers and facilitators to implementation of VETPALS in the VA, Investigator study staff (Drs. [name], [name], [name]) will conduct structured interviews with the site study coordinators, VETPALS facilitators, and peer facilitators at the study conclusion. These interviews will assess the time commitment required to lead each group, the administrative procedures used, and any local clinical or organizational factors that facilitated or hindered recruitment, scheduling, retention, or delivery of the intervention.

Focus Groups

To better understand any barriers and facilitators to implementation from the Veteran's perspective, we will conduct 2-4 focus groups in the final year of the study (additional details in *3.0 Objectives*). Focus groups will be facilitated by Investigator-level study staff using guided questions to ascertain treatment, psychological, and organizational and logistical factors that may have affected participation.

Staff Research Interviews

To better understand any barriers and facilitators to implementation from the research staff perspective, we will conduct individual interviews with site study coordinators and VETPALS facilitators. Investigator-level study staff (Drs. [name], [name], and [name]) will conduct structured interviews with these staff to assess time commitment required to lead each group, administrative procedures used, and any local clinical or organizational factors that facilitated or hindered recruitment, scheduling, retention, or delivery of the educational programs.

Table 2: Assessment Timeline

See Appendix E for a copy of all measures and interview questions.

	Measure	Screening	Baseline	Treatment Completion	Month 6 Follow-Up
Screening					
Mental Status	SPMSQ	X			
Primary Outcomes					
Physical Functioning	MFA-SF		X	X	X
Psychosocial Functioning	PHQ-9		X	X	X
Secondary Outcomes					
Quality of Life	WHQOL-BREF		X	X	X
Positive Affect	PANAS		X	X	X
Intermediate Outcomes					
Self-Efficacy	MSES		X	X	X
Patient Activation	PAMS		X	X	X
Problem Solving	SPSI-R		X	X	X
SM Stages of Change	SOC		X	X	X
Prosthesis Use	Prosthesis Use		X	X	X
Potential Covariates					
Memory	RBANS		X		
Fluency/Executive Function	COWAT		X		
Attention	Digit Span		X		
Comorbidity	FCI		X		
Pain	CPG		X	X	X
Complications	Chart Review		X	X	X
Social Support	MSPSS		X	X	X
Alcohol Use	AUDIT-C		X	X	X
Smoking Status	CHQOER Ques.		X	X	X
Implementation Variables					
Treatment Engagement*	PTCS			X	
Treatment Fidelity*	Audio Recording Review		Ongoing		
Use of Supplementary Resources	Checklist			X	
Satisfaction	Checklist			X	
Implementation Barriers (Facilitator)*	Focus Group				Project Completion
Implementation Barriers (Participant)	Focus Group			Subsample	

* Completed by Study Staff

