Enrolled participants are assigned on a rolling basis into successive cohorts of 8±2 individuals at each participating site. Each time 8±2 participants are enrolled, that cohort will be randomized 1:1 to receive either the VETPALS intervention or individual education support program (control condition). We will ensure that participants will not have completed a PALS program prior to study participation and will not be part of an existing PALS group during their study participation. Randomization will occur through an email exchange between the study sites (VETPALS facilitator or site PI) and the data manager at Spectrum Research. The data manager will maintain a randomization table that is stored locally on a server at Spectrum Research. When a cohort is ready for randomization, the facilitator or site PI will send an email to the data manager stating that a group of participants is ready for randomization. The email will also include a list of study ID numbers but will not contain any information that could identify participants. Within 12-24 hours of receiving the email, the data manager will verify the list of study IDs in the database to ensure all baseline assessments are complete, and then will obtain random assignment by accessing the randomization table. The data manager will respond via email to the facilitator or site PI with a value of 0 or 1 (0=individual education support program, 1=VETPALS). Both parties will retain a copy of the email for reference. The data manager will record the treatment assignment for the group in the randomization table, and the facilitator or site PI will record the treatment assignment in the randomization log. This method will ensure that treatment allocation is concealed during the recruitment of each cohort. A balanced number of groups will be randomly assigned to each site based on the projected enrollment at that site, which is a common randomization schedule used in group-based interventions. The randomization schedule and algorithm will not be shared with local sites to maintain concealment of treatment allocation. Additionally, the data manager will record a value of 0 or 1 to each study ID in the database which is linked to the study ID assigned at enrollment. Clinical research staff at each location (applicable investigators and VETPALS facilitators) will receive the treatment allocation and randomization ID in order to proceed with the treatment, intervention or control. Site study coordinators who conduct the baseline and follow-up assessments are blind to treatment.

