Participants will complete follow-up assessments with study coordinators in-person or by telephone at 6 weeks and 6 months. Study coordinators will screen for any anticipated and unanticipated adverse events at scheduled follow-up visits and by telephone contact with participants at 3 weeks and 18 weeks. Coordinators will briefly call participants to check-in, do a few medical review questions, and give a reminder of the next study appointment. Coordinators who cannot reach participants by phone at 3 or 18 weeks for the medical review questions should alert another site researcher who can complete the assessment by medical record review in CPRS. At the end of the study, coordinators will conduct a final 1-year medical record review. Study coordinators do not access the medical record until all follow-ups are complete at the end of the study in order remain blind to intervention assignment.

[figure not shown]
Additional details of the assessments and a study flow sheet can be found in the protocol document. Participants will receive reminders via telephone and mail for upcoming study visits from the study coordinator. The baseline assessment will take up to 60 minutes to complete and follow-up assessments will take up to 30 minutes to complete. Study coordinators remain blinded to treatment condition throughout the entire study and will be trained to ensure consistent and optimal administration of the assessments, as well as on strategies to remain blinded from treatment (e.g. strategies to remind patients not to reveal treatment).

Randomization

As described on page 21, this is a two-arm randomized controlled trial. The treatment allocation will automatically be matched to the study ID in the online randomization system. Clinical research staff at each location (site PIs and VETPALS facilitators) will receive the treatment allocation and proceed with study related activities for both conditions. Again, site study coordinators who conduct the baseline and follow-up assessments are blind to treatment.

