Participants will be randomized to a treatment group (group-based program/intervention vs. individual education program/control) following completion of the baseline assessment (see 5.1 Study Design). The site study coordinators will be naïve to treatment allocation throughout all of the assessments to minimize potential bias of the outcomes.

Group based self-management program (VETPALS Intervention)

Participants randomized to the intervention group will be asked to complete a checklist about their use of supplementary class resources, a checklist about their satisfaction with the classes, and selected participants will be invited to participate in a focus group to respond to and discuss implementation variables. The site PIs and VETPALS facilitator have primary responsibility in overseeing data collection on paper forms. Data will be entered into the central study database by the site PIs and/or VETPALS facilitator via eCRF. In the event a participant doesn't receive

any necessary materials during class sessions, a facilitator will mail materials to the participant and will include a return postage-paid addressed envelope if needed. Participants randomized to the intervention group are offered the other program at the end of their 6-month follow-up assessment. Study coordinators will record (yes/no) patients who elect to participate in the individual program and will refer patients to the facilitator who will discuss the other program and scheduling in more detail.

We will use a digital voice recorder to audio-record the VETPALS sessions. The purpose of audio-recording the VETPALS sessions is to monitor treatment fidelity, assess feedback, and ensure protocol adherence. Each participating site will consult with the local R&D office to ensure that the digital audio-recorder meets local VA guidelines, and all recorders will use FIPS 140-2 validated encryption. Sites will use the device(s) listed in the local site Central IRB applications.

Individual education support program (Control)

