Participants randomized to the control group will not have any additional assessments or evaluations to complete. In the event a participant doesn't receive any necessary materials during the individual education support program, a facilitator will mail materials to the participant and will include a return postage-paid addressed envelope if needed. Participants in the control group are offered the VETPALS intervention classes at the end of their 6-month follow-up assessment. Study coordinators will record (yes/no) patients who elect to participate in the intervention classes and will refer patients to the facilitator who will discuss the other program and scheduling in more detail.

Patients who are randomized but unable to begin VETPALS or the Individual Education Support Program

In the event a participant is randomized but cannot begin participating in the assigned intervention, the participant will be given several options. There may be unexpected circumstances (e.g. personal or family illness, change in job status, personal situation) that may prevent a participant from starting the assigned intervention with their cohort as originally planned. VETPALS facilitators will discuss options with the participant.

1. The participant can be included in the same randomized intervention at a later date. The facilitator will wait for the next cohort that is assigned the same intervention and will contact participants to determine if they can participate with the next cohort.
2. If the participant agrees to be included in the next cohort, the facilitator will notify the study coordinator of this change so the study coordinator can include the participant in all subsequent follow-up assessments. The facilitator will only share the participant's study ID number so the coordinator remains blinded to treatment.
3. Participants may be asked to complete a second baseline assessment with the study coordinator. This will be assessed on an individual participant basis and site investigators and the PI will use their discretion when deciding if a second baseline should be completed. Collecting the baseline data again prior to starting the intervention

ensures that the research data reflects the most current responses. Participants who complete a second baseline will receive \$20 for their time and participation.

Periodic medical record review

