Site study coordinators will conduct a brief medical review at scheduled assessments (baseline, 6 weeks, and 6 months) and at 3 weeks, 18 weeks, and 1 year. Site study coordinators will call participants by telephone at these intervals to do a brief medical screening to capture all anticipated and unanticipated adverse events. Site study coordinators will alert another site researcher to complete the assessment via medical record review for participants who cannot be contacted by phone. This ensures the study coordinator will remain blind to treatment assignment. At the end of the study, coordinators will conduct a final 1-year medical record review. Site study coordinators will record any anticipated adverse events, including complications such as stump non-healing, revision amputation, contralateral amputation, and mortality. For individuals who undergo a revision or new amputation, we will calculate the time in days since the qualifying event (original amputation). See 6.0 Reporting for a list of all anticipated AEs. Periodic medical record review allows study coordinators to also check for any UAE or SAEs. All data are collected on an eCRF using the EDC system.

Complications and anticipated AEs include stump non-healing, revision to same or higher level, contralateral amputation, and mortality. These will be monitored and collected during the subjects' hospital stay and after discharge by systematically reviewing the subject's medical record at designated intervals and during formal follow-up interviews at 6 weeks and 6 months.

Follow-up

All participants will complete follow-up assessments at approximately 6 weeks after randomization (coinciding with the end of the intervention sessions) and at 6 months. Similar to the baseline assessment, site study coordinators conduct follow-up interviews in-person or by phone, whichever is most convenient for the participant. All follow-up data are collected using EDC on VA approved and secure laptop and desktop computers and assessments take up to 30 minutes to complete. A list of the measures used at baseline and follow-up are found in the *assessment measures* section and in Table 2.

Temporary changes: Baseline, periodic medical record review, and follow-up

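### Recording the crossover choice by programme name tells the blinded coordinator the arm of cohort-mates whose 6-month assessment is still pending

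*Combined protocol and SAP*

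**What the plan says.** All of the following is in the combined protocol and SAP.

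- **Unit of randomisation (5.1 Study Design).** "Each time 8±2 participants are enrolled, that cohort will be randomized 1:1". Every member of a cohort therefore has the same arm.
- **Blinding (5.1).** "Study coordinators remain blinded to treatment condition throughout the entire study". The Randomization paragraph of 5.5 likewise says the coordinators do not know the allocation during any of the assessments.
- **Who assesses (5.5, Follow-up).** "site study coordinators conduct follow-up interviews in-person or by phone".
- **Offer and record, control arm (5.5).** "Participants in the control group are offered the VETPALS intervention classes at the end of their 6-month follow-up assessment", and then "Study coordinators will record (yes/no) patients who elect to participate in the intervention classes".
- **Offer and record, VETPALS arm (5.5).** "Participants randomized to the intervention group are offered the other program at the end of their 6-month follow-up assessment", and then "Study coordinators will record (yes/no) patients who elect to participate in the individual program".
- **After the record (5.5, both arms).** The coordinator refers the participant to the facilitator, who discusses and schedules the second programme.

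**The concern.** The programme named in the coordinator's record is the opposite of the one the participant received, so the entry identifies the arm. For the participant just interviewed this does no harm, because the 6-month data are already in. The harm falls on cohort-mates. They share the allocation, and some may not yet have had their own 6-month interview with the same coordinator.

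Participants, facilitators and site PIs all know the arm, so masking of the coordinator is the only masking of outcome assessment that the plan describes. Hypotheses 1a and 1b both include the 6-month change in MFA-SF and PHQ-9. If the procedure runs as written, the trial report could not state without qualification that 6-month assessment was blinded.

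**Working it through.** **Step 1. Does the route exist on the text?** Four conditions are needed.

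1. One allocation per cohort: yes (5.1).
2. The coordinator knows who is in the cohort: yes. Coordinators schedule baselines as a cohort fills (5.1) and notify the site PI and facilitator when its baselines are complete (8.0 Privacy and Confidentiality).
3. The coordinator handles an arm-specific record: yes, in both arm subsections of 5.5.
4. The record can precede a cohort-mate's 6-month interview: yes. The offer is tied to each participant's own visit, and nothing delays it to the cohort's last visit or gives the record to other staff.

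Other routes are guarded. Coordinators do not open charts until follow-up is complete, and controls learn their arm from other staff (both 5.1). For deferred participants only the study ID is passed on (5.5). No such guard covers this route.

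**Step 2. Reproduce the plan's own counts.** Groups in Table 1 (5.2): Seattle 12, Cleveland 12, Houston 15, Tampa 12, Minneapolis 8.

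- 12 + 12 + 15 + 12 + 8 = 59 groups
- Enrolled: 59 × 8 = 472, as stated
- Retained: 59 × 6 = 354 = 472 × 0.75, as stated

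The Statistical Power text in 5.6 gives 51 cohorts instead: 51 × 6 = 306 completers. That discrepancy is a separate matter and does not change the share below.

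**Step 3. Share of 6-month assessments made after the first offer in the cohort.** With k completers, of whom b are assessed before the first offer is recorded, the share is (k − b)/k. For k = 6:

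| b | Share exposed |
|---|---|
| 1 (strictly sequential) | 5/6 = 83% |
| 2 | 4/6 = 67% |
| 3 | 3/6 = 50% |
| 6 (all seen together) | 0% |

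The strictly sequential case gives 59 × 5 = 295 of 354, or 51 × 5 = 255 of 306. For cohorts of 6 to 10 and retention of 75% to 100%, the sequential share runs from (4.5 − 1)/4.5 = 78% to (10 − 1)/10 = 90%.

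**Step 4. Bias, as illustration only.** The documents give no interviewer effect and no split between interviewer-read and self-completed assessments. Let d be the between-arm difference in interviewer effect, in SD of change, and s the share of exposed assessments delivered by the interviewer. The shift in the arm contrast is then d × s × 5/6.

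- Assumed d = 0.1, s = 0.25: 0.1 × 0.25 × 5/6 = 0.02 SD
- Assumed d = 0.2, s = 1: 0.2 × 1 × 5/6 = 0.17 SD

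For scale, with 177 completers per arm (354/2) and the plan's ICC of 0.01 to 0.10, the standard error √[(2/177)(1 + 5 × ICC)] is 0.11 to 0.13 SD. If the interviewer effect is equal in both arms, d = 0 and there is no bias.

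**The case against.** The strongest reply is that the leak may lie in the prose and not in the form. The record is a yes/no. Section 5.5 elsewhere refers to the alternative programme in neutral terms, and the offer is written in the passive, so no text says the coordinator makes it. The arm-specific names sit in subsections written for a reader who knows the arm. Appendix E, which holds the forms, is not in the text available. Section 5.1 also trains coordinators to remind participants not to reveal their treatment. This stands in part: a reader might infer that the coordinator cannot complete the record without learning the arm, and the documents do not establish that. A single neutral field would avoid it. But the recording sentences name both the coordinator and the programme, and no instruction makes the field neutral.

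Four other stronger readings are tempting and not supported.

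- *Masking is lost for most of each cohort.* That needs near-sequential visits. Visit order is not stated, and 5.5 allows group sittings at baseline and describes follow-up as similar.
- *Six months is the main time point for the primary outcomes.* Only the paragraph on hypotheses 2a-e in 5.6 ranks 6 months first. For 1a and 1b both times are listed without rank.
- *Most outcomes are read aloud by the coordinator.* Section 5.5 allows phone interviews or self-completion at a computer, and gives no proportions. Both primary outcomes are fixed-response self-reports, which limits what an interviewer can do.
- *A second cohort is unmasked through a deferred participant.* Section 5.5 makes this possible, since such a person joins a later cohort of the same arm and the coordinator is told. No number of deferrals is given, so it is not counted here.

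**Conclusion.** Wrong as written: the promised assessor blinding is contradicted by the plan's own procedure for recording the crossover choice. The exposed data are the 6-month assessments of participants whose cohort-mate has already been offered the other programme. A participant's own 6-month data and the cohort's 6-week data are not affected by this route.

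The extent lies between 0 and 5 of every 6 completers. The upper end assumes 6 completers per cohort, strictly sequential visits, and a record made in the words of section 5.5. The direction and size of any bias cannot be derived from the documents. Bias needs an interviewer effect that differs by arm, and it would act mainly through phone or coordinator-read interviews. The conclusion rests on the contradiction and not on the illustrative SD figures.

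**What to change.** Amend the two arm subsections of 5.5 so that the facilitator or site PI makes the crossover offer and records the yes/no. Both already receive the allocation, and the facilitator already arranges the second programme. Remove the coordinator's recording and referral steps. At the end of the 6-month visit the coordinator says only that another team member will call. Keep the field on a form that the coordinator's login cannot open; the user privileges described in 8.0 already allow this.

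The cost is protocol wording, one change of form access, and a short call by staff who make the follow-on contact anyway.

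Waiting to make the offer until the cohort's last 6-month assessment is optional. Early finishers would wait a little longer, and the timing would have to be checked against section 5.1 (Potential Risk/Benefit Analysis), where participants are told they may have the other programme once their own programme and follow-up are done.

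If 6-month visits have already taken place under the current text, the report should qualify the blinding claim for them.
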